### 7.1.7 Clinical Laboratory Tests

Summary statistics (N, mean, standard deviation, median, minimum, and maximum) will be tabulated for hematology, serum chemistry and urinalysis. For the minimum and maximum summary statistics, the minimum and maximum results taken during any assessment within cohort will be used.

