22.10.2 Safety Laboratory Tests

Analyses of safety laboratory data will be performed in the following manner:

- Summary tables of safety laboratory parameters will be provided by Study Cohort and overall.
- Box-Plots of laboratory measurements before study IP administration and afterwards by scheduled visit and will be provided. In this analysis baseline values are the measurements taken up study IP administration,

while “during trial” evaluations are the measurements taken after that time point.

- Descriptive statistics of quantitative tests results and changes from baseline by scheduled visit will also be provided. The analysis algorithm as described for the above Box-Plots assessments will be used for this analysis as well.
- Quantitative laboratory measurements will be categorized with reference to the normal ranges as Low, Normal, or High. Shift analysis of the categorical change from baseline to each scheduled visit and to the last observed assessment will also be performed.
- A list of parameters and related cut-off values defining the potentially clinically significant (PCS) abnormal values will be outlined by the Sponsor. Measurements used in the analysis are those taken following study IP administration. The incidence tables of PCS lab values as well as the individual patient listing will be provided using the denominator which is the number of subjects with at least one post-baseline administration of trial medication. Individual subjects’ listings of PCS measurements will also be presented.

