22.10.3 Vital Signs

Analyses of vital signs (blood pressure, pulse, temperature, and respiration rate) will be performed in the following manner:

- Summary tables of vital signs will be provided by Study Cohort and overall.
- Box-Plots of vital signs before study IP administration and afterwards by scheduled visit and will be provided. In this analysis baseline values are the measurements taken up study IP administration, while “during trial” evaluations are the measurements taken after that time point.
- Descriptive statistics of quantitative tests results and changes from baseline by scheduled visit will also be provided. The analysis algorithm as described for the above Box-Plots assessments will be used for this analysis as well.
- A list of parameters and related cut-off values defining the potentially clinically significant (PCS) abnormal values will be outlined by the Sponsor. Measurements used in the analysis are those taken following study IP administration. The incidence tables of PCS lab values as well as the individual patient listing will be provided using the denominator which is the number of subjects with at least one post-baseline administration of trial medication. Individual subjects’ listings of PCS measurements will also be presented.

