#### 4.1.2 Baseline and Change from Baseline

Unless indicated otherwise, change from baseline (CFB) will be calculated as follows, where the baseline assessment is the last assessment before OpRegen injection:

$$\text{CFB} = \text{Value at Visit} - \text{Baseline}$$

Percent change from baseline (PCFB) will be calculated as follow:

$$\text{PCFB (\%)} = 100 * (\text{Value at Visit} - \text{Baseline}) / \text{Baseline}$$

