### 7.1.8 Vital Signs

Summary statistics (N, mean, standard deviation, median, minimum, and maximum) will be tabulated for vital sign parameters by cohort and overall. N will be calculated as the number of subjects with  $\geq 1$  assessment for the given parameter. For the minimum and maximum summary statistics, the minimum and maximum results taken during any assessment within cohort and overall will be used.

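### SAP 7.1.7–7.1.8 specify no by-visit change, laboratory shift or PCS analysis for laboratory tests and vital signs, and take minima and maxima over any assessment, including those before implantation

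*SAP*

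**What the plan says.** Protocol 22.10.2 (laboratory tests) and 22.10.3 (vital signs) each plan box plots before and after implantation, and by-visit summaries: "Descriptive statistics of quantitative tests results and changes from baseline by scheduled visit will also be provided". Each also plans incidence tables and listings of PCS values against sponsor-defined cut-offs. For the PCS analysis the protocol states: "Measurements used in the analysis are those taken following study IP administration". Laboratory values are also to be classed against the normal range: "Shift analysis of the categorical change from baseline to each scheduled visit and to the last observed assessment will also be performed".

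SAP 7.1.7 and 7.1.8 give a single set of statistics: N, mean, SD, median, minimum and maximum. The laboratory rule is: "For the minimum and maximum summary statistics, the minimum and maximum results taken during any assessment within cohort will be used". The vital-sign rule is: "For the minimum and maximum summary statistics, the minimum and maximum results taken during any assessment within cohort and overall will be used". For vital signs, "N will be calculated as the number of subjects with" at least one assessment of the parameter. Neither section mentions scheduled visit, baseline, change, normal range, shift or PCS.

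SAP 4.1.2 defines change from baseline in general terms, where "the baseline assessment is the last assessment before OpRegen injection". SAP 7.1.10 names change from baseline for BCVA, low-luminance BCVA and IOP.

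On endpoints, Protocol 7.3.1 lists 12 entries for treatment-emergent change. SAP 3.2.1 lists IOP alone.

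**The concern.** Treatment-emergent change in laboratory values and vital signs is a protocol safety endpoint under the primary objective. The data are collected for that comparison. Protocol 14.1.2 takes laboratory tests as a pre-implantation baseline and again after treatment. SAP Table 1 says the physical examination and vital-sign assessments serve to judge the subject's condition before and after implantation, including the safety of immunosuppression.

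A programmer following SAP 7.1.7–7.1.8 literally would produce extremes that mix the two periods. That programmer would have no instruction to tabulate change by visit, laboratory shifts or PCS incidence. The clinical study report could then lack the displays that the protocol planned for this endpoint.

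**Working it through.** No sample size, power or error rate bears on this point, and there is no stated figure to reproduce. The check compares texts and counts entries.

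**Same version.** SAP 2.0 says it is based on protocol amendment 14, which is the protocol at hand. No text is blacked out in SAP 7.1.7 or 7.1.8.

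**Analyses side by side.**

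| Analysis | Protocol 22.10.2 (labs) | Protocol 22.10.3 (vitals) | SAP 7.1.7–7.1.8 | SAP Section 11 titles |
|---|---|---|---|---|
| Value and change by scheduled visit | yes | yes | not specified | not named |
| Shift from baseline | yes | not planned | none | none |
| PCS incidence, post-implantation values | yes | yes | none | none |
| Box plots | yes | yes | none | Figures 14.3.2.1-7 and 14.3.3.1 may be these |

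Shift (1) + PCS (2) = 3 planned analyses with no SAP text and no named output. Change by visit adds 2 that are not specified for these data, although SAP 4.1.2 defines the quantity.

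For labs and vitals, Section 11 lists 2 tables (14.3.2, 14.3.3.2), 7 + 1 = 8 figures and 2 listings (16.3.2, 16.3.3).

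**The minimum and maximum rule.** Assessments exist on both sides of implantation: Protocol 14.1.2 and 11.3.1 place laboratory tests before it, and 11.3.1 also places vital signs there. Taken over any assessment, the reported maximum is max(largest pre-implantation value, largest post-implantation value), and the minimum is the mirror image. The printed figure does not say which period supplied it. The visit schedule is blacked out, so how often a pre-implantation value would supply the extreme cannot be computed.

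**The other statistics.** The vital-sign N counts subjects with any assessment, so it is not a per-visit N. The SAP does not say which assessments enter the mean, SD and median.

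**Endpoint list.** Protocol 7.3.1 has 3 general entries (vital signs; haematology, chemistry and urinalysis; physical examination) and 9 ophthalmological ones: 3 + 9 = 12. SAP 3.2.1 keeps IOP: 12 − 1 = 11 not named there. These divide as follows:

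- 5 appear in SAP 3.2.4 as efficacy parameters: BCVA, SD-OCT, microperimetry, FAF and CFP.
- 3 have an analysis section in SAP 7.1.7–7.1.9: laboratory tests, vital signs and physical examination.
- 3 appear in neither place: dilated fundus examination, slit lamp and FA. SAP Table 1 still marks all three as safety.

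Check: 5 + 3 + 3 = 11.

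**The protocol's PCS denominator.** It is worded "using the denominator which is the number of subjects with at least one post-baseline administration of trial medication". A single implantation has no post-baseline administration, so this needs rewording when the analysis is restored.

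**The case against.** The strongest reply is that this is brevity. SAP 4.1.2 defines change from baseline for general use. Section 11 titles are generic: those for BCVA and IOP mention neither visit nor change, yet SAP 7.1.10 specifies change over time for both. Table shells exist that the reader cannot see. Individual values will be listed, by visit where appropriate. Protocol 14.1 routes clinically significant out-of-range laboratory results to adverse events, and systemic-toxicity adverse events have their own table. The trial has 24 subjects, no formal testing, and a protocol (22.1) that lets the SAP modify its plans.

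Much of this stands. Silence in a title proves little, so the point rests on the text of 7.1.7–7.1.8. The shells or figures may show change by visit, and individual histories can be read from the listings. The reply does not reach the any-assessment rule, which is an explicit instruction, or the absence of any shift or PCS text. Adverse event reporting depends on investigator judgement and does not replace incidence against fixed cut-offs.

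Three stronger readings are tempting, and the documents do not support them:

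- That every statistic is pooled over time. The SAP says so only for the minimum and maximum, and implies it for the vital-sign N.
- That the SAP abandons 11 of 12 safety endpoints. The count holds for section 3.2.1 alone; eight of the 11 are covered in 3.2.4 or 7.1.7–7.1.9. That the blacked-out text after IOP hides no further entry is an inference from the singular wording.
- That the protocol limits all these analyses to post-implantation data. That limit belongs to the PCS analysis; change from baseline needs pre-implantation values.

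**Conclusion.** The point holds for labs and vitals. As specified, the minimum and maximum cannot show whether an extreme arose before or after implantation, and no specified table shows treatment-emergent change. Three protocol analyses are missing from the SAP text and its named outputs, and two more are left unspecified. Listings, adverse event reporting and possible box plots reduce the loss without removing it.

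The endpoint list is a smaller, separate inconsistency: three safety assessments marked in SAP Table 1 appear in neither SAP 3.2.4 nor SAP 7.1.7–7.1.9.

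The conclusion assumes that the any-assessment rule means what it says and that the unseen shells do not supply the missing analyses. If the shells show change by visit, that part becomes a documentation gap, and the minimum and maximum rule would still need correcting. The matter should be settled before database lock.

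**What to change.** In SAP 7.1.7–7.1.8, using the SAP 4.1.2 baseline:

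- Tabulate observed value and change from baseline by scheduled visit, by cohort and overall, with N, minimum and maximum within visit. State the time basis of every statistic.
- Limit any worst-value summary across visits to post-implantation data.
- Restore the laboratory shift tables to each scheduled visit and to the last observed assessment.
- Restore PCS incidence for laboratory tests and vital signs from post-implantation values. Use as denominator the subjects with at least one post-implantation measurement of that parameter.
- Name these outputs in Section 11.

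Reconcile SAP 3.2.1 with Protocol 7.3.1 and SAP Table 1, or justify the reduction. Protocol 22.1 allows the SAP to modify the plan but requires a protocol amendment if the modification is major, so an amendment arises only if the reduction is kept and judged major.

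The cost is SAP text and programming. The data are already part of the planned collection.

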### 7.1.8 Vital Signs

Summary statistics (N, mean, standard deviation, median, minimum, and maximum) will be tabulated for vital sign parameters by cohort and overall. N will be calculated as the number of subjects with  $\geq 1$  assessment for the given parameter. For the minimum and maximum summary statistics, the minimum and maximum results taken during any assessment within cohort and overall will be used.

### 7.1.9 Physical Exam

The number and percentage of subjects with abnormal physical exam results by system organ class at the [REDACTED] will be tabulated by parameter for each cohort and overall.

### 7.1.10 Efficacy Analyses

All efficacy data will be listed for all subjects. Efficacy summaries will be presented for the Intent to Treat Population for all variables.

- Directional change in the geographic atrophy ([GA](#)) lesion area over time
- Overall change in the [GA](#) lesion area of the study eye over time using [FAF](#)
- Change from baseline over time in [BCVA](#) as measured by Early Treatment Diabetic Retinopathy Study ([ETDRS](#)) chart
- Change from baseline over time in Low Luminance [BCVA](#)
- Change from baseline over time in [IOP](#)

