6.6 SUBRETINAL ROUTES OF ADMINISTRATION

6.6.1 Vitrectomy and Retinotomy

The subretinal implantation of cells is customarily accomplished with a conventional partial vitrectomy followed by retinotomy. Pars plana vitrectomy (PPV) has become an important tool in vitreoretinal surgery and in the treatment of retinal disease. The traditional 3-port procedure is well-known to retina specialists and is performed with microsurgical equipment resulting in incisions that are usually self-sealing. The vitreous is gently removed with a vitreous cutter and the cell suspension of OpRegen is implanted subretinally through a small retinotomy. The wound is self-healing. The procedure can be visualized through the dilated pupil with a special wide-field lens. Although vitrectomy is useful to diagnose and treat many retinal diseases, it is not without challenge, most notably clouding of the lens as a result of perturbations to the vitreous and potential egress of implanted cells through the retinotomy site until healed.

[REDACTED]

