22. STATISTICAL METHODOLOGY

22.1 STUDY DESIGN AND SAMPLE SIZE

As this is an open-label, phase I/IIa dose escalation, safety, tolerability and preliminary efficacy study, neither power assessment, nor formal hypotheses testing are currently planned for study outcome measures.

Detailed methodology for data summary and analyses will be documented in a Statistical Analysis Plan (SAP). This document may modify the plans outlined in the protocol; however, any major modification of the outcome measures and/or its analysis will also be reflected in a protocol amendment. Additional statistical analyses other than those described in this section may be performed if deemed appropriate and included in the SAP.

The planned sample size of approximately 24 eyes for 4 study cohorts to be treated with targeted OpRegen® doses of 50×10^3 and up to 200×10^3 cells, is considered clinically appropriate for further characterization of the safety, tolerability and preliminary efficacy of OpRegen® in the treatment of subjects with subjects with advanced dry-form AMD with GA.

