22.12.1 Efficacy Endpoints of Clinical Relevance

Preliminary efficacy assessments will utilize the below listed parameters:

- Directional change in the GA lesion area over time
- Overall change in the GA lesion area of the study eye over time using SD-OCT and FAF
- Change from baseline over time in BCVA as measured by ETDRS chart
- Change from initial assessment over time in retinal sensitivity (as assessed by microperimetry)
- Change from baseline over time in Reading Speed Test
- Change from baseline over time in Low Luminance BCVA
- Correlation assessment between quantitative metrics derived from FAF images, SD-OCT images and CFP images
- Correlation assessment between functional and structural changes
- Change over time in NEI VFQ-25 Quality of Life score
- Change over time in Functional Reading Independence (FRI) Index score

[REDACTED]

[REDACTED]

[REDACTED]

[REDACTED]

- [REDACTED]
 - [REDACTED]
 - [REDACTED]
- [REDACTED]
- [REDACTED]

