#### 3.2.4 Efficacy Endpoints of Clinical Relevance

Preliminary efficacy assessments will utilize the below listed parameters:

- Directional change in the geographic atrophy ([GA](#)) lesion area over time
- Overall change in the [GA](#) lesion area of the study eye over time using [SD-OCT](#) and [FAF](#)
- Change from baseline over time in [BCVA](#) as measured by Early Treatment Diabetic Retinopathy Study ([ETDRS](#)) chart
- Change from initial assessment over time in retinal sensitivity (as assessed by microperimetry)
- Change from baseline over time in Reading Speed Test
- Change from baseline over time in Low Luminance [BCVA](#)
- Correlation assessment between quantitative metrics derived from [FAF](#), [SD-OCT](#) and [CFP](#) images
- Correlation assessment between functional and structural changes
- Change over time in National Eye Institute Visual Function Questionnaire-25 ([NEI VFQ-25](#)) Quality of Life ([QoL](#)) score
- Change over time in Functional Reading Independence ([FRI](#)) Index score

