Physical Examination including ECG, Vital Signs Clinical evaluation by the study-dedicated investigator or designee will be performed at several time points to evaluate pre- and post-implantation subject condition including immunosuppression treatment safety (see below)**		√	
Malignancy Assessment In the case of any suspected malignancies at screening, subject should be referred to appropriate medical specialist.		√	
Complete Blood count (including differential) / Chemistry (including Serum Electrolytes) / Coagulation / Urinalysis		√	
Serology Assessment including testing for HIV, CMV, EBV , HBV and HCV		√	
[REDACTED]		√	
Immunology		√	

Assessment	Time points	Primary Endpoints/ Safety	Efficacy Endpoints of Clinical Relevance
HLA-typing will be performed during [REDACTED] or during one of the subsequent visits if not performed during [REDACTED]			
[REDACTED]	[REDACTED]	√	
QuantIFERON (state of inoculation) To detect tuberculosis (TB) disease	[REDACTED]	√	
[REDACTED]	[REDACTED]	√	
Fundus Autofluorescence Imaging (FAF) Images obtained by certified examiner (technician acceptable). Reading of images done by central reading center. Images are done by using blue light Heidelberg instrumentation. Each assessment for each subject must be done with the same camera used at Screening. Refer to Central Reading manual for instructions.	[REDACTED]	√	√
Color Fundus Photography (CFP) Images obtained by certified examiner (technician acceptable). Reading of images done by central reading center. Color Images are done by using Zeiss instrumentation. Each assessment for each subject must be done with the same camera used at Screening. Refer to Central Reading manual for instructions.	[REDACTED]	√	√
Reading Speed Test This test is mandatory for subjects are proficient in English.	[REDACTED]		√
NEI VFQ-25 Quality of Life (examiner version) 25 item subject reported outcome. Scores range from 0-100 with the higher score indicating better visual function.	[REDACTED]		√

Assessment	Time points	Primary Endpoints/ Safety	Efficacy Endpoints of Clinical Relevance

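### SAP 7.1.10 summarises overall GA-area change by FAF alone, without explanation, although SAP 3.2.4 and the protocol define that endpoint by SD-OCT and FAF

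*SAP*

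**What the plan says.** The protocol gives the endpoint in Section 22.12.1 as "Overall change in the GA lesion area of the study eye over time using SD-OCT and FAF". The Synopsis and Section 7.3.4 say the same.

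The SAP repeats the two-modality definition in its endpoint section, 3.2.4: "lesion area of the study eye over time using [SD-OCT](#) and [FAF". Its Table 1 marks both SD-OCT and FAF as efficacy assessments.

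SAP 7.1.10 then lists the efficacy variables to be summarised. There the overall GA-area item reads "lesion area of the study eye over time using [FAF", with no mention of SD-OCT. The companion item, "Directional change in the geographic atrophy ([GA](#)) lesion area over time", names no modality.

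**The concern.** The section that tells the programmer what to produce is narrower than the endpoint it is meant to serve. A programmer working from 7.1.10 would build the GA table, figures and annual-rate output from FAF only, and nothing elsewhere in the SAP would prompt a second set of results.

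Timing makes this more than an untidy sentence. The SAP was written when open-label data already existed. If one of two stated modalities disappears from the summary at that stage without explanation, a reader of the study report cannot tell whether the result shown was the planned one or one of two that were available. GA area is also the only structural measure with its own efficacy table, figures and listings in SAP Section 11, so the ambiguity falls on the structural result that readers will look at.

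**Working it through.** No formula applies: the documents give no sample-size or power calculation for this endpoint. The check is a comparison of texts and dates.

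**1. Modality named for overall GA-area change**

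| Place | SD-OCT | FAF |
|---|---|---|
| Protocol Synopsis, efficacy endpoints | yes | yes |
| Protocol 7.3.4 | yes | yes |
| Protocol 22.12.1 | yes | yes |
| SAP 3.2.4 | yes | yes |
| SAP 7.1.10 | no | yes |

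All 4 endpoint definitions name both modalities. The single analysis list names one.

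**2. Whether another output restores SD-OCT.** SAP 7.0 says results will be presented as set out in Section 11. The GA outputs there are Table 14.2.1, Figures 14.2.1.1 and 14.2.1.2, and Listings 16.2.1.1 and 16.2.1.2. None states a modality, and no table, figure or listing in Section 11 names SD-OCT. The endpoint that would have put the modalities side by side, "Correlation assessment between quantitative metrics derived from [FAF](#), [SD-OCT](#) and [CFP](#) images", stands in SAP 3.2.4 but is not carried into 7.1.10.

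**3. Whether SD-OCT was singled out.** SAP 3.2.4 lists 10 efficacy endpoints. SAP 7.1.10 carries 4 of them (directional GA change, overall GA change, BCVA, low-luminance BCVA) and adds IOP. The other 10 − 4 = 6 are absent: microperimetry, reading speed, the two correlation assessments, NEI VFQ-25 and FRI. The list is incomplete in general.

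**4. Timing.** SAP version 1.0 is dated 12 October 2022 and rests on protocol Amendment 14 of 9 April 2019, about three and a half years earlier. SAP 4.0 describes all four cohorts as already treated: 3 + 3 + 6 + 12 = 24 subjects. SAP 6.0 says in the past tense that interim reports including efficacy data went to the DSMB. Protocol 20.2 confirms that the study is open label and that the sponsor was not blinded to the data supplied to the DSMB.

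**5. Availability of images.** In the protocol's visible screening, pre-implantation and follow-up visit lists, SD-OCT and FAF appear together, both marked for central reading. No new acquisition would be needed.

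**The case against.** The strongest reply is that this is a drafting slip with little consequence. The SAP is labelled an initial draft, so there is no previous SAP against which to see a change. It keeps both modalities in 3.2.4 and in Table 1, which a deliberate switch would hardly leave in place. The same list drops six other endpoints, which suggests haste rather than selection against SD-OCT. Section 7.1.10 also promises that all efficacy data will be listed, and all efficacy analysis is descriptive.

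Most of this stands as an account of how the text may have arisen. It does not remove the contradiction. A general promise of listings is not a summary of a stated endpoint, and Section 11 identifies no SD-OCT listing.

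A reader might infer three stronger things that the documents do not support:

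- **That FAF was chosen because of the results.** The documents show that data existed before the SAP was written. They do not show that SD-OCT results influenced its wording.
- **That the protocol's amendment rule was broken.** Protocol 22.1 lets the SAP modify the plan and adds that "any major modification of the outcome measures and/or its analysis will also be reflected in a protocol amendment". Amendment 14, which the SAP cites, still names both modalities. Whether narrowing one unranked, descriptive endpoint is a major modification is a matter of judgement.
- **That FAF is biased in treated eyes.** SAP Table 1 says of FAF that "Images are done by using blue light Heidelberg instrumentation", and Protocol 6.6.1 lists among the challenges of vitrectomy "most notably clouding of the lens as a result of perturbations to the vitreous". Neither document links lens clouding, or the implanted cells, to measured GA area. Neither gives a direction of error or ranks SD-OCT above FAF. The SAP introduction also describes a second delivery route besides vitrectomy, so the lens remark cannot be extended to all 24 eyes.

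**Conclusion.** The point holds as an unexplained inconsistency between the SAP's analysis section and both its own endpoint section and the protocol. Its size is one of two stated modalities left without a named summary, for 24 treated eyes and their fellow eyes, in every GA output. The consequence is ambiguity and a risk of selective reporting. No error rate or power figure changes, because no formal testing is planned.

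The conclusion rests on reading 7.1.10 as the operative list of efficacy summaries, which is how the SAP presents it. It does not depend on why SD-OCT is missing: the same correction is needed whether the omission was accidental or intended. GA area is treated here as prominent because of its place in Section 11; the documents do not rank the efficacy endpoints.

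**What to change.** In SAP 7.1.10, name both SD-OCT and FAF for overall GA-area change. In Table 14.2.1, Figures 14.2.1.1 and 14.2.1.2, and Listings 16.2.1.1 and 16.2.1.2, state the modality and give results by each one, for treated and fellow eyes.

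If FAF alone is intended, record it as a change from SAP 3.2.4 and the protocol, with its date and reason, and report SD-OCT as a sensitivity result. No rule that the two modalities must agree is needed: the analysis is descriptive and neither document sets a success criterion for it.

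The cost is SAP wording and a second set of columns. The images are already acquired and sent for central reading. One assumption should be confirmed with the reading center: that GA area was graded on SD-OCT at these visits, since the grading manual is not among the documents. The other downside is that the two modalities may disagree and give a less tidy result.
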